A Comparison of Horizontal and Vertical Bitewing Radiographs in Detecting Approximal Caries and Interdental Bone Loss in Posterior Teeth: A Diagnostic Accuracy Randomized Cross-Over Clinical Trial

NCT04341636

February 20, 2020

Principal Investigator:

[name]

Departments of Dental Public Health and Periodontology
King Abdulaziz University, Tufts University, Harvard University

Co-Investigators:

[name], [name]
Faculty of Dentistry, King Abdulaziz University

1. Background and Rationale

Bitewing radiographs are a standard diagnostic tool in dental practice, primarily used to detect approximal caries and evaluate interproximal alveolar bone levels. Traditionally, horizontal bitewings have been widely used for these purposes. However, they have limitations in visualizing vertical bone loss, furcation involvement, and root caries.

Vertical bitewing radiographs, by contrast, provide greater visibility of the apico-coronal dimension and root structures, making them potentially more effective for diagnosing periodontal conditions and deeper carious lesions. This study aims to compare the diagnostic accuracy of vertical versus horizontal bitewing images in detecting caries and bone loss in posterior teeth.

2. Objectives

Primary Objective

- To compare the accuracy of vertical versus horizontal bitewing radiographs in detecting approximal caries and alveolar bone loss.

Secondary Objective

- To evaluate the effectiveness of both imaging modalities in identifying furcation involvement.
- To assess the diagnostic clarity and patient suitability for each radiographic approach.

Material and methods:

3. Study Design

This is a two-arm, randomized crossover clinical trial comparing vertical and horizontal bitewing radiographs. The study was conducted at the Faculty of Dentistry, King Abdulaziz University.

Type of Study: Open-label, randomized crossover clinical trial

Study Setting: Faculty of Dentistry, King Abdulaziz University

Registration: ClinicalTrials.gov (NCT04341636)

Ethical Approval: KAU Ethics Committee (#053-06-17)

4. Participants

Inclusion Criteria:

- Age ≥ 18 years
- Presenting for treatment at KAU dental clinics
- Presence of posterior teeth and canines in each quadrant
- No acute periodontal infection
- Non-smokers
- Full ability to open mouth and tolerate X-ray procedures

Exclusion Criteria:

- Systemic conditions complicating treatment
- Pregnancy or lactation
- Prosthesis obscuring CEJ or caries borders

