- Gag reflex or any contraindication to X-ray
- Refusal to participate

5. Interventions

Each participant received:

- Four horizontal bitewing radiographs (control)
- Four vertical bitewing radiographs (experimental)
- Radiographs were taken using a standardized film holder and a 3-mm orthodontic wire attached to the sensor for magnification calibration.

Observers included two restorative specialists (for caries) and two periodontists (for bone loss), all blinded to group assignments.

6. Measurements

- Caries Assessment:

Evaluated using a 5-point diagnostic confidence scale and a secondary clarity scale.

- Bone Loss & Furcation:

Measured from the CEJ to the alveolar crest using calibrated software. Furcation involvement was assessed using a 5-point scale.

- Intra- and Inter-Observer Agreement:

Evaluated with Kappa statistics and intra-class correlation coefficients.

7. Sample Size Calculation

- **Software:** G*Power 3.1.9

- Effect size: 2.1 mean difference

- SD: 5.2

- Power: 80%

- Alpha: 0.05

- Required Sample: 20 patients

8. Statistical Analysis

Statistical Analysis

Software:

Data will be analyzed using IBM SPSS Statistics version 23.0 (IBM Corp., Armonk, NY, USA) and ROC analysis will be performed using MedCalc or equivalent software for diagnostic

accuracy assessment.

8.1 Analysis Population:

All radiographs captured for the 20 enrolled participants (160 total bitewing images: 80 vertical, 80 horizontal) will be included. Both intention-to-treat and per-protocol analyses will be conducted. All images were anonymized, and evaluators were blinded to image type and patient identity.

8.2 Primary Analysis:

Primary Endpoints:

- Detection of approximal caries (presence and clarity)
- Alveolar bone level measurements (in mm)
- Presence and clarity of furcation involvement

Tests for Diagnostic Accuracy:

- **Receiver Operating Characteristic (ROC) Analysis:**

ROC curves were plotted for each evaluator for both vertical and horizontal bitewings.

The Area Under the Curve (AUC) was computed to assess diagnostic accuracy compared to the “gold standard” (combined clinical and radiographic diagnosis).

- AUC values close to 1.0 indicate higher accuracy.
- Comparisons of AUCs between vertical and horizontal bitewings were conducted using DeLong’s test.
- **Sensitivity and Specificity:** These were calculated for each radiographic method in detecting caries and furcation involvement. 95% confidence intervals were provided.

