8.3 Observer Reliability:

- **Intra-Observer Agreement:** Measured using **Weighted Kappa coefficients** for repeated readings of the same radiographs by the same observer at two time points.

- **Inter-Observer Agreement:** Measured using **Intraclass Correlation Coefficient (ICC)** for bone level measurements and **Weighted Kappa** for caries and furcation rating scores between observers.

Interpretation of Kappa values:

- < 0.20: Poor
- 0.21–0.40: Fair
- 0.41–0.60: Moderate
- 0.61–0.80: Substantial
- 0.81–1.00: Almost perfect

8.4 Comparative Tests Between Vertical and Horizontal Bitewings:

- **Wilcoxon Signed-Rank Test:** Used to compare the mean alveolar bone loss measurements (mesial, distal, and total) between vertical and horizontal bitewings (non-parametric paired comparison).
- **McNemar Test:** Applied to assess paired binary outcomes (e.g., presence vs. absence of caries or furcation involvement) between imaging modalities.
- **Chi-Square Test:** Used to compare proportions of overlapping contacts and furcation detection in both modalities.
- **Descriptive Statistics:**
 - Mean \pm standard deviation (SD) for continuous variables (e.g., bone level)
 - Frequencies and percentages for categorical variables (e.g., tooth type, gender distribution)

8.5 Handling of Missing Data:

- Missing image evaluations (if any) were addressed via sensitivity analysis using pairwise deletion, given the minimal expected rate due to controlled data acquisition and blinded

scoring.

8.6 Effect Size Reporting:

- For Wilcoxon and McNemar tests, effect sizes (r) were reported.
- For ROC analysis, 95% CI of AUCs and comparison P-values were provided.

9. Expected Outcomes

- Vertical bitewings will show higher sensitivity in detecting furcation involvement.
- Vertical bitewings will provide better diagnostic accuracy for approximal caries and alveolar bone loss.
- Vertical bitewings will have superior intra- and inter-observer reliability in detecting pathology.

10. Ethical Considerations

- All participants provided informed written consent.
- Ethical approval was secured from local ethics board.
- All data were anonymized and securely stored.
- Participants had the right to withdraw at any time without consequences.

11. Timeline

Phase	Duration
Ethical Approval	Completed
Participant Recruitment	2 months
Radiograph Collection	2 months
Data Analysis	1 month

Phase	Duration
Manuscript	1 month

12. Dissemination Plan

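### The primary objective promises accuracy for alveolar bone loss, but every analysis that names bone level omits a reference, and the one between-modality test (Wilcoxon) detects only a shift

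*Combined protocol and SAP*

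**What the plan says.** - **Section 2, primary objective:** "To compare the accuracy of vertical versus horizontal bitewing radiographs in detecting approximal caries and alveolar bone loss". Section 9 expects vertical images to be the more accurate for both targets.
- **Section 5, readers:** "Observers included two restorative specialists (for caries) and two periodontists (for bone loss), all blinded to group assignments".
- **Section 6, bone measurement:** "Measured from the CEJ to the alveolar crest using calibrated software". Caries and furcation each get a 5-point scale; bone gets only this distance.
- **Section 8.2, endpoints and ROC:** bone level in millimetres is a primary endpoint. "ROC curves were plotted for each evaluator for both vertical and horizontal bitewings", and "Comparisons of AUCs between vertical and horizontal bitewings were conducted using DeLong’s test". The gold standard is described only as "combined clinical and radiographic diagnosis". Neither ROC statement names a target condition. Sensitivity and specificity are listed for caries and furcation, not for bone loss.
- **Section 8.3:** bone level enters an inter-observer ICC, which measures reliability.
- **Section 8.4:** the Wilcoxon signed-rank test is "Used to compare the mean alveolar bone loss measurements (mesial, distal, and total) between vertical and horizontal bitewings". Bone level also appears in the descriptive mean and SD. The McNemar test compares presence or absence calls between modalities, with caries and furcation as its examples.

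**The concern.** Accuracy means closeness to a reference. Bone loss is one of the two targets of the primary objective, yet each analysis that names bone level (Wilcoxon, ICC, mean and SD) compares readings with each other or merely describes them. The ROC analysis in 8.2 could supply the missing comparison, and the raw millimetre readings could enter it without a cut-off. It needs a true state for each site, however, and the plan does not say which sites count as bone loss or which radiographs feed the gold standard.

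If the bone-loss conclusion is drawn from the test that names it, a significant Wilcoxon result could be reported as better accuracy when vertical images simply over-read. A real gain in precision could equally go unseen. If the analyst instead fills the ROC gap after seeing the data, the choice of reference can decide which modality wins.

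**Working it through.** The plan gives no figure to reproduce on this point. From the documents: 20 patients, paired readings, and a partly radiographic gold standard. Everything else below is assumed for illustration.

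**Model.** Truth = 2.5 mm + patient effect (SD 0.8) + site effect (SD 0.8). Reading = truth + bias + patient-level error (SD 0.2) + site error. There are 16 sites per patient (results for 8 in brackets). The Wilcoxon test is applied to the 20 patient means of D = vertical − horizontal, over 4,000 runs.

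**Step 1: what the Wilcoxon test can see.** In D the truth cancels. D has mean bias(V) − bias(H), and its patient-mean variance is 2 × 0.2² + (site variance V + site variance H)/sites. No term says which reading is nearer the truth.

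**Step 2: precision gain without bias.** Site error SD is 0.4 (vertical) v 1.0 (horizontal).
- Mean absolute error = √(2/π) × total error SD.
- Vertical: 0.798 × √(0.04 + 0.16) = 0.36 mm. Horizontal: 0.798 × √(0.04 + 1.00) = 0.81 mm.
- Mean of D = 0. Wilcoxon p < 0.05 in 4.2% (4.7%) of runs, which is the chance level.

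**Step 3: two opposite truths.** Site error SD is 0.5 in both modalities.
- Vertical +0.3, horizontal 0: mean of D = 0.3 − 0 = 0.3.
- Vertical 0, horizontal −0.3: mean of D = 0 − (−0.3) = 0.3.
- In both cases, with 16 sites, the variance of the patient mean is 0.08 + 0.50/16 = 0.111 and the SD is 0.33. D has the same distribution in each.

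| Truth | Vertical found larger | Mean absolute error, V v H (mm) |
|---|---|---|
| Vertical over-reads by 0.3 | 96% (91%) | 0.495 v 0.430 |
| Horizontal under-reads by 0.3 | 95% (91%) | 0.429 v 0.494 |

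The test result is the same, but the more accurate modality differs. The AUCs are equal in both cases, because a constant shift does not change ranks. An AUC comparison would therefore not detect this bias either.

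**Step 4: does ROC close the gap?** That depends on the reference. Assume a clinical reading with error SD 0.5 mm, averaged equally with the horizontal reading and called positive at 3.0 mm or more, with an AUC comparison clustered by patient.
- Vertical more precise (0.4 v 1.0): AUC about 0.90 for vertical v 0.96 for horizontal. The comparison favours the less precise horizontal images in about 81% (55%).
- Equal precision (0.5 each), 16 sites: it falsely favours horizontal in about 96%.

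The horizontal reading's own error is inside the reference, so horizontal agrees with it by construction.

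**Step 5: secondary, McNemar in 8.4.** Without conditioning on the reference, it compares positive-call rates. Assume 80 reference-positive and 240 reference-negative sites.
- Equal sensitivity 0.70, specificity 0.85 (V) v 0.95 (H): expected positive calls are 56 + 36 = 92 v 56 + 12 = 68. Vertical makes more calls and detects no more disease.
- Vertical better on both (sensitivity 0.75 v 0.60, specificity 0.95 v 0.90): 60 + 12 = 72 v 48 + 24 = 72. The calls are equal although vertical is superior.

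**The case against.** The strongest reply is that 8.2 already covers bone loss. Bone level is a listed primary endpoint, the diagnostic-accuracy tests follow directly, ROC curves are drawn for each evaluator, and two evaluators are periodontists reading bone loss. The ROC text names no target for caries or furcation either. The plan also keeps the Wilcoxon test under a separate heading and never calls it a test of accuracy.

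Much of this stands. A reader might infer that bone loss is excluded from ROC, that it has no accuracy analysis at all, or that no gold standard exists. The documents support none of these: a generic gold standard is stated, and the ROC text may include bone loss. The omission specific to bone loss is in the sensitivity and specificity line, together with the absence of any bone-loss case definition or reference measurement. Nor does the plan say that its accuracy conclusion will rest on the Wilcoxon test; that is only the risk if the test naming bone level is used.

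A reader might also infer that writing down a case definition is enough, because AUC would then show any precision gain. With an error-free reference and site error SD 0.4 v 1.0, the clustered AUC comparison favours vertical in 97.7% to 99.9% of runs with 16 sites. That is not evidence for the remedy. It assumes a perfect reference and one wide contrast; at 0.4 v 0.5 the figure is about 21%. With a reference fed by horizontal images, the comparison can reverse.

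**Conclusion.** The point holds in this form: accuracy for bone loss is promised, no analysis that names bone level uses a reference, and the reference that ROC would need is not defined for bone loss. The Wilcoxon test cannot support an accuracy conclusion in either direction. This follows from its construction, since the truth cancels in the paired difference; the simulated percentages (about 5% and about 95%) only illustrate it.

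Those percentages, and the 81%, 55% and 96% for a contaminated reference, rest on assumed reader errors, site counts and reference construction. The documents give none of these, and they do not say that horizontal images feed the gold standard, only that it is partly radiographic. Because one of the two targets of the primary objective is affected, this should be settled before any bone-loss accuracy claim is made. The McNemar point is separate and of lower priority.

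**What to change.** **Option 1: an independent reference exists.** If bone loss was recorded by site in a way that does not use the horizontal or vertical images being compared (for example, the clinical component of the gold standard), state that case definition. Name bone loss as a target of the 8.2 ROC/AUC comparison on the raw millimetre readings. Use patient-clustered inference, for example by resampling whole patients, and note that AUC does not detect a constant bias. Do not use a reference fed by the compared images. Cost: SAP wording and one further AUC comparison on data already collected, with less precision if few sites have bone loss.

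**Option 2: no such reference exists.** Restate the bone-loss part of the primary objective and of Section 9 as between-modality agreement. Report the mean paired difference and limits of agreement with patient clustering, and state that these do not show which modality is closer to the truth. Cost: a primary objective is restated and the bone-level conclusion becomes more modest.

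**In either case,** do not interpret the Wilcoxon result as evidence of accuracy.

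**Secondary.** To compare sensitivity and specificity for caries and furcation, run McNemar separately in reference-positive and reference-negative sites, with patient-clustered 95% confidence intervals. This uses the same data.

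### The Section 8.4 tests for caries and furcation compare how often each view is called positive, not how often it is right, and no paired comparison of sensitivity or specificity is named

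*Combined protocol and SAP*

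**What the plan says.** The primary objective in Section 2 is "To compare the accuracy of vertical versus horizontal bitewing radiographs in detecting approximal caries and alveolar bone loss". Section 8.2 lists caries detection and "Presence and clarity of furcation involvement" among the primary endpoints.

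Two sections of the plan compare the views on these outcomes:

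- **Section 8.2, Primary Analysis.** "The Area Under the Curve (AUC) was computed to assess diagnostic accuracy compared to the" reference standard, defined as "combined clinical and radiographic diagnosis". The AUCs of the two views are compared with DeLong's test. Sensitivity and specificity for caries and furcation are calculated for each view with 95% confidence intervals. No between-view test of either is named, and the ROC text does not say which endpoints it covers.
- **Section 8.4, Comparative Tests.** McNemar's test is "Applied to assess paired binary outcomes (e.g., presence vs. absence of caries or furcation involvement) between imaging modalities". The chi-square test is "Used to compare proportions of overlapping contacts and furcation detection in both modalities". Neither entry mentions the reference diagnosis.

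Section 8.6 asks for an effect size for McNemar, so its result is meant to be reported as a comparison. Section 9 expects that "Vertical bitewings will show higher sensitivity in detecting furcation involvement".

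**The concern.** An extra positive call is a gain at a diseased site and an error at a healthy one. A paired test on raw calls adds the two together, so its result has no fixed meaning for accuracy, which is what the trial sets out to compare.

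The gap matters because these are the only between-view tests named for the binary calls themselves. Separate confidence intervals for each view's sensitivity do not test the paired difference, and DeLong's test concerns the whole ROC curve. No named test therefore addresses the Section 9 expectation about furcation sensitivity. If the McNemar result and the Section 8.2 results point in different directions, the plan leaves the authors to choose between them after seeing the data.

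**Working it through.** **Inputs.** The plan gives no number of sites, prevalence, sensitivity or specificity, so there is no planned figure to reproduce. The Section 7 sample size is stated for a mean difference and has no bearing here. Everything below rests on assumed values: N = 200 sites, D = 30 diseased, and readings of the two views independent given true status. H is horizontal, V is vertical, Se is sensitivity and Sp is specificity.

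**Formulas.**

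- Expected positives = D·Se + (N − D)·(1 − Sp)
- Positive on V only: b = D·Se_V·(1 − Se_H) + (N − D)·(1 − Sp_V)·Sp_H
- Positive on H only: c = D·Se_H·(1 − Se_V) + (N − D)·(1 − Sp_H)·Sp_V
- McNemar chi-square = (b − c)² / (b + c)

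**Case 1: significant through false positives alone.** Se = 0.80 in both views; Sp = 0.95 (H) and 0.85 (V).

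- Positives: H 24 + 8.5 = 32.5; V 24 + 25.5 = 49.5.
- b = 4.8 + 24.2 = 29.0; c = 4.8 + 7.2 = 12.0.
- Chi-square = 17² / 41.05 = 7.04, p = 0.008, in the direction of V.
- Correct calls: H 24 + 161.5 = 185.5; V 24 + 144.5 = 168.5. V is the less accurate view.
- Split by reference status: diseased sites 4.8 versus 4.8, no difference in sensitivity; healthy sites 24.2 versus 7.2, chi-square = 17² / 31.45 = 9.19, p = 0.002, against V.

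**Case 2: no difference although V is better on both measures.** H: Se 0.60, Sp 0.85. V: Se 0.80, Sp 0.885 (1 − 19.5/170).

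- Positives: H 18 + 25.5 = 43.5; V 24 + 19.5 = 43.5.
- b = 9.6 + 16.6 = 26.2; c = 3.6 + 22.6 = 26.2. The expected McNemar contrast is zero.

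**Case 3: a threshold shift that AUC cannot show.** Both views share one equal-variance binormal ROC curve. H is read at Se 0.65, Sp 0.95. V is read at Sp 0.85, where Se is 0.84.

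- Separation = 0.385 + 1.645 = 2.03. AUC = Φ(2.03/√2) = 0.924 for both views, so DeLong's test has nothing to find.
- Positives: H 28.0; V 50.7. b = 33.0, c = 10.3. Chi-square = 22.7² / 43.4 = 11.9, p = 0.0006.
- Of the 22.7 extra positive calls, 25.5 − 8.5 = 17 are false positives, about 75%.

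**Range.** With Se 0.70 in both views and Sp 0.95 (H) against 0.80 (V), over prevalence 0.10 to 0.40, the p-value on positive calls runs from 0.000001 to 0.004 with 320 sites and from 0.016 to 0.15 with 80 sites. At every point in that range V has more positive calls and fewer correct ones.

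**Clustering.** These p-values treat sites as independent. In Case 1, significance at 5% is lost once the variance is inflated by more than 7.04/3.84 = 1.83. With 200 sites in 20 patients, 10 each, that is an intra-patient correlation of about 0.83/9 = 0.09. The direction does not change.

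**The case against.** A reader might infer that a view that over-calls disease would be reported as the better one. The documents do not support that. No rule says that more positives means better, and Section 8.2, the section headed as primary, judges both views against the reference. In Case 1 the specificity intervals it requires would be about 91–97% and 79–90% (Wilson, 170 healthy sites). They do not overlap, so the over-calling would be visible. In Case 3 the AUCs agree, but reported specificity would still show the shift.

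A reader might also infer that readers' expectations would push up calls on the vertical view. Section 8.1 states that evaluators are blinded to image type, so that argument is not available.

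Other points on that side are fair. The example in the McNemar entry is not exhaustive, and the entry does not state the site set. Section 9 lists expectations rather than formal hypotheses, and furcation is a secondary objective in Section 2, although Section 8.2 lists it as a primary endpoint. Case 2 was tuned so that the counts cancel.

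What remains is that the outcome actually named for McNemar is the raw call. Per-view intervals and an AUC test do not supply the missing paired comparison of sensitivity and specificity, and the order of precedence is unstated.

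**Conclusion.** The point holds in this form: the McNemar test and the chi-square test on furcation detection in Section 8.4 are not tied to the reference, do not test accuracy, and could contradict the accuracy results in Section 8.2, with nothing in the plan to say which governs. It does not follow that the trial's conclusion would be wrong, because the primary analysis is reference-based and could expose over-calling.

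The logic needs no assumptions. The size does: p = 0.008 in Case 1 rests on assumed prevalence, accuracy, number of sites and independence, and it would not survive moderate clustering within patients. It illustrates what can happen and does not forecast this trial. The point also takes the reference in Section 8.2 as given. The change is worth making because it fills a real gap in the analysis of named endpoints at very little cost.

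**What to change.** In Section 8.4:

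- Replace the comparison of raw calls with a paired, McNemar-type comparison run separately in reference-positive sites (difference in sensitivity) and reference-negative sites (difference in specificity), for caries and for furcation.
- Define a positive call by one cut of the relevant 5-point scale, fixed in advance and identical for both views.
- Allow for sites clustered within patients.
- Use this in place of the chi-square test on furcation detection, and report raw detection counts descriptively only.
- State that the reference-based comparisons decide which view is more accurate.

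The cost is SAP wording and a re-split of data that the study already collects. The real price is precision: each comparison uses fewer sites, so intervals widen and p-values become less favourable. In Case 2 the split comparisons would give 9.6 versus 3.6 in diseased sites (chi-square = 6² / 13.2 = 2.73, p = 0.10) and 16.6 versus 22.6 in healthy sites (chi-square = 6² / 39.15 = 0.92, p = 0.34), before any allowance for clustering. Both point the right way, but neither is significant with 30 diseased sites.

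### Section 8.4 assigns a chi-square test to overlapping contacts and furcation although the readings are paired and clustered within patient, and it states no analysis unit and no rule on which furcation test counts

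*Combined protocol and SAP*

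**What the plan says.** Sections 3 and 5 describe a crossover in which each participant receives four horizontal and four vertical bitewings. Section 8.1 counts 160 images from 20 participants, 80 per modality.

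Section 8.4 then lists two tests for binary outcomes:

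- McNemar: "Applied to assess paired binary outcomes (e.g., presence vs. absence of caries or furcation involvement) between imaging modalities".
- Chi-square, in the next bullet: "Used to compare proportions of overlapping contacts and furcation detection in both modalities".

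Furcation therefore appears under both tests. Caries appears only under McNemar. Overlapping contacts appear only under chi-square.

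Section 8.2 lists "Presence and clarity of furcation involvement" among the primary endpoints. Overlapping contacts are not a listed objective or endpoint.

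Section 8.6 adds: "For Wilcoxon and McNemar tests, effect sizes (r) were reported". It does not mention chi-square.

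On the data behind these tests, section 6 says for caries "Evaluated using a 5-point diagnostic confidence scale and a secondary clarity scale" and for furcation "Furcation involvement was assessed using a 5-point scale". Section 5 says: "Observers included two restorative specialists (for caries) and two periodontists (for bone loss), all blinded to group assignments". No section says whether the unit for the binary tests is the site, tooth, image or patient, or how scores and readers are reduced to one yes/no result.

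**The concern.** An ordinary chi-square test on two proportions treats the vertical and horizontal readings as coming from unrelated samples. Here they come from the same mouths and largely the same sites. McNemar handles the pairing, but in its ordinary form it assumes that the pairs are independent of one another. Several pairs from one patient need not be.

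Three things are at stake:

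- The stated error rate of the binary comparisons may be wrong, in a direction that cannot be known in advance.
- For furcation, a listed primary endpoint, two tests may give two answers and the plan does not say which one is reported as the result.
- Because the unit is not stated, a reader cannot tell whether the McNemar test for caries and furcation is sound or not.

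**Working it through.** **Inputs from the documents.** 20 patients, 4 images per modality: 20 × 4 = 80 per modality and 20 × 8 = 160 in all, which agrees with section 8.1. Alpha is 0.05 (section 7). The documents give no detection rates, correlations or number of sites per patient, and no figure for any binary comparison, so there is no plan figure to reproduce.

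**The three statistics.** Let N be the number of site pairs, p_V and p_H the proportions positive, p̄ their mean, b the vertical-only positives and c the horizontal-only positives. For patient i, let d_i be vertical-only minus horizontal-only positives.

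- Chi-square: (p_V − p_H)² / [2p̄(1 − p̄)/N]
- McNemar: (b − c)² / (b + c)
- Clustered McNemar: (Σd)² / Σd², on 1 df

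The last two have the same numerator, because Σd = b − c. Expanding the squares, Σd² = (b + c) + the cross-products between different sites of the same patient. Those cross-products are what ordinary McNemar leaves out. They vanish on average when the modality difference does not vary between patients, and they vanish exactly when each patient supplies one pair.

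**The choice of test can change the conclusion.** Take 80 hypothetical pairs: 20 positive on both, 16 vertical only, 6 horizontal only, 38 on neither. Then p_V = 36/80, p_H = 26/80 and p̄ = 62/160.

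- Chi-square = (10/80)² / [2 × (62/160) × (98/160)/80] = 2.63, p = 0.105.
- McNemar = (16 − 6)²/(16 + 6) = 100/22 = 4.55, p = 0.033 (exact p = 0.052).

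This treats the 80 pairs as independent and only illustrates the lack of a precedence rule.

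**Error rates under assumed inputs.** Simulated data with no true modality difference: 20 patients, 25% positive, a latent normal score with variance shares of 0.2 for patient and 0.2 for site, a patient-by-modality share v, and the rest residual. The share v measures how far the modality difference varies between patients. Four readings per modality correspond to one per image; 16 is an assumed site count. Rejection rates at nominal 5%:

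| Readings per modality | v | Chi-square | Site-level McNemar | Clustered McNemar; paired t on patient proportions |
|---|---|---|---|---|
| 4 | 0 | about 2.5% | about 5% | about 5% |
| 4 | 0.1 | about 4% | about 8% | about 5% |
| 4 | 0.2 | about 7% | about 11% | about 5% |
| 16 | 0 | about 2.5% | about 5% | about 5% |
| 16 | 0.1 | about 13% | about 19% | about 5% |
| 16 | 0.2 | about 23% | about 30% | about 5% |

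At v = 0 the number of sites makes no difference. More sites amplify the error only when v is above 0.

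**Sensitivity to the site share.** With a site share of 0.5 and 4 readings, chi-square rejects in 0.8 / 2.0 / 4.1% at v = 0 / 0.1 / 0.2, and site-level McNemar in 5.1 / 9.2 / 13.3%. The stronger the pairing, the more conservative chi-square becomes, while the clustering problem in McNemar remains.

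**If the patient is the unit.** Ordinary McNemar on one yes/no result per patient (any positive site) rejects in about 1-5%, so it is not inflated.

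**The case against.** Several points on the other side have force.

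- *Chi-square might mean McNemar's chi-square.* That it means the unpaired test is an inference, drawn from McNemar having its own bullet that refers to pairing. If both bullets meant McNemar, the second would be redundant for furcation, and the missing unit and clustering method would remain.
- *The mention of r for McNemar in section 8.6 signals that McNemar governs.* It is a hint, but it does not state precedence.
- *Chi-square is merely conservative.* That is true when the modality difference is constant across patients, and at 4 readings with v = 0.1 it is still below 5%. It does not hold generally.
- *Accuracy is assessed elsewhere.* This stands. Section 8.2 compares accuracy by ROC curves and DeLong's test, per evaluator, and needs no cut-off on the 5-point scale. The tests in section 8.4 compare detection rates between modalities. A reader might infer that the main accuracy comparison is undermined; this point gives no support for that.
- *Overlapping contacts are exploratory.* This also stands, and it lowers the weight of the part where chi-square is the only named test.

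A reader might also infer that McNemar is the wrong test for caries. The documents do not show that: with one result per patient it would be sound. The defect for caries is the unstated unit, and caries has no two-test conflict.

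**Conclusion.** The point holds on the text. A chi-square test is named for outcomes that are paired by design, furcation has two tests and no rule of precedence, and no unit or clustering method is given for any binary outcome. That much is certain, apart from the inference that chi-square means the unpaired test.

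The size is not certain. With the modality difference constant across patients, chi-square is conservative (about 2.5%, or under 1% with a site share of 0.5) and site-level McNemar is close to 5%. With a patient-by-modality share of 0.1 to 0.2, the rates are about 4-7% and 8-11% at four readings per modality, and about 13-23% and 19-30% at 16 sites. All of these rest on assumed prevalence, variance shares and site counts; they show what can happen and do not estimate this trial's error rate.

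Two stronger readings should be avoided. Many sites per patient do not by themselves inflate either test; variation of the modality difference between patients is required. Rejection rates near 40% can be produced, but only with 16 assumed sites and a patient-by-modality share of 0.4, twice each of the patient, site and residual shares. Nothing in the documents supports that value.

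The change should be made. It concerns the detection-rate comparisons in section 8.4 and does not call the trial as a whole into question. Furcation's differing status, a secondary objective in section 2 and a primary endpoint in section 8.2, is a separate matter.

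**What to change.** Delete the chi-square bullet in section 8.4. For each binary outcome (overlapping contacts, furcation presence, caries presence) pre-specify one paired test that treats the patient as the cluster. Either of these serves:

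- clustered McNemar, (Σd)² / Σd² on 1 df, with d the vertical-only minus horizontal-only positives per patient; or
- a Wilcoxon signed-rank test (already used in section 8.4 for bone levels) or a paired t test on patient-level proportions.

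Deleting chi-square alone is not enough, because site-level McNemar can also exceed 5%.

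Report the paired difference in proportions with a cluster-adjusted 95% confidence interval. State the analysis unit, and the single reader rule and cut-off that produce the yes/no result entering the test. Parts of the plan are written in the past tense; if images have already been read, date the change and disclose its timing.

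The cost is a short SAP change and slightly more analysis work. Intervals may be wider than from an unclustered McNemar analysis. No extra patients, images or readers are needed.
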